### 8.4: Normal end to the study

At the end of the 8-week intervention, subjects completing that part of the study will be followed for another 36 weeks with encouragement to maintain their assigned home practice. Questionnaires will be completed at 22 weeks post-intervention (Visit 13) and 36 weeks post intervention (Visit 16).

## 9. STATISTICAL CONSIDERATIONS

---

### 9.1: General Design Issues

This study is a planning grant for development of an adequately powered clinical trial. Statistical hypotheses are not considered relevant to this mechanism. Randomization is designed to assess feasibility of our randomization plan, in addition to general feasibility issues of the delivery of the educational programs.

In our third aim, we proposed exploratory analysis of clinical outcomes (see below).

## 9.2: Sample Size and Randomization

### 9.2.1: Treatment Assignment Procedures

Participants are randomized to treatment assignments to test the acceptability of randomization in the population. Random allocation, stratified by gender, is assured by a computer-generated assignment accessible to the REDCap administrator, but group assignment cannot be masked, except to quantitative data analysts.

**Power and sample size.** Untreated, >30% of adolescents are expected to develop incident depression. Power is calculated for time to incident MDD. With a sample size of 80, we expect to have 80% power to detect a hazard ratio of 0.52 for time to MDD between the groups. It is anticipated that we will screen 160 with the QIDS and 120 with the DISC to achieve a sample of 80 eligible teens (with 80 parents). Our target recruitment estimate is 53 females and 27 males, based on research demonstrating that there are twice as many female teens with subsyndromal depression as males. **Note that all enrollment figures refer to teens.** Each will have the involvement of one parent.

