## 9.5: Outcomes

Our primary goal is to develop a depression-prevention program based on mindfulness and self-compassion and to establish the feasibility of its implementation as compared with an active attention-control comparator. Hence, the establishment of quality assurance processes and complete data documentation assume even greater importance than data analysis. Data of multiple types from multiple sources will be captured. For questionnaire assessments, secure internet-based data collection instruments will be used, accessible by internet-capable device.

Quality assurance of these measures will include review of study instruments for range and consistency checks, and descriptive analyses to assess distributions of study variables. Quality assurance of qualitative measures include 1) maintaining a spreadsheet to log scheduled, completed, transcribed, and analyzed focus groups and interviews; 2) establishing a transcription template to ensure data is uniform in appearance; 3) arranging for secure storage of recordings and transcripts on REDCap; 4) review of consistency of styles across interviewers; and 5) review of recordings to assess accuracy of transcriptions.

All statistical analyses will utilize all adolescents who were randomized to one of the intervention arms and who attended at least one class. Individuals who were unable to attend a class are excluded. Complete case analyses are planned (without imputations).

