### 9.5.1: Primary Outcome

For the primary outcome, (to be explored as described in Specific Aim 3, once feasibility is examined in Specific Aim 2), a score of 70 on the PROMIS Pediatric Depression Scale short form t-score. To assess incident depression, we will use exploratory nonparametric (Kaplan-Meier plots) and semi-parametric analyses (Cox proportional hazards models) to examine the trends in incident depression within and between treatment arms. If too few students reach the target of 70 (2 standard deviations above the population mean), we will explore outcomes using a target of 65 (1.5 standard deviations above the population mean). We had originally planned to use the SMFQ, but the SMFQ was collected only 5 times for those with complete data and the PROMIS Depression score was collected weekly, making it a much more reasonable measure for a time-to-event analysis.

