## 9.6: Data Analyses

### 9.6.1 Exploratory analyses of outcomes and mediators.

Exploratory analyses will involve first examining variable distributions and missing data patterns. Next, we will conduct exploratory analyses to assess patterns of change associated with participation in the programs. The study is not expected to produce a quantity of data large enough to have adequate power to detect significant effects of the MFY program compared to the TFY control program. However, trends in incident depression (primary outcome, PROMIS Pediatric Depression Scale), change in depression scores (combined SMFQ-C, PROMIS Pediatric Depression Score) resilience (secondary outcome), and potential mediators will be examined by program arm.

To assess incident depression, we will use exploratory nonparametric (Kaplan-Meier plots) to examine the trends in incident depression within and between treatment arms using the PROMIS Pediatric Depression Scale short-form..

To address the change in depressive symptoms (secondary outcome), we will examine the paired t-test in each condition, to test for any effect of either program. Subsequently, an exploratory analysis will examine the trajectory of changes over time by program arm, using graphical representations of outcomes at each time point by subject, cohort, and program arm as well as longitudinal random effects models. Hence, a within-group model would include terms for the follow-up depression score, the overall intercept, the cohort effect, the time effect, and a cohort\*time interaction—to allow the trajectory to vary by cohort—as well as random effects for individual subjects and subjects nested within cohorts.

Additional explorations will include bivariable associations (correlation, simple regressions) between the process measures and the outcome, between intervention assignment and process measures, between intervention assignment and potential mediators, and between process measures and outcomes. If indicated, mediation analyses will be conducted to investigate possible mechanisms; strength of mediation (indirect effect) will be calculated as the product of the association of the causal variable on the mediator and the association of the mediator on the outcome variable.

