## 7.2 Justification of Sample Size

Our primary goal is to refine our programs based on mindfulness and self-compassion to prevent MDD among adolescents and to establish the feasibility of its implementation as compared with an active attention-control comparator. Data of multiple types (focus group

recordings, questionnaires) will be captured with attention to complete data capture through frequent participant contact.

**Power and sample size.** Untreated, >30% of adolescents are expected to develop incident depression. Power is calculated for time to incident MDD and change in depressive symptoms. With a sample size of 80, we expect to have 80% power to detect a hazard ratio of 0.52 for time to MDD between the groups as well as >80% power to detect a mean difference of 4 (SD 6) in SMFQ-C + SMFQ-P. It is anticipated that we will screen 160 with the QIDS and 120 with the DISC to achieve a sample of 80 eligible teens (with 80 parents). Our target recruitment estimate is 53 females and 27 males-based on research demonstrating that there are twice as many female teens with subsyndromal depression as males. **Note that all enrollment figures refer to teens.** Each will have the involvement of one parent.

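### The stated 80% power for a hazard ratio of 0.52 with 80 teens needs about 74 events; control incidence of 30% to 60% gives about 19 to 39 events and 29% to 53% power

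*Combined protocol and SAP*

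**What the plan says.** Section 9.2.1 bases its power statement on one rate and one effect size. The rate is "Untreated, >30% of adolescents are expected to develop incident depression", with no upper bound and no time horizon. The effect claim is "With a sample size of 80, we expect to have 80% power to detect a hazard ratio of 0.52 for time to MDD". Alpha, sidedness, the number of events and any allowance for dropout are not given. Section 7.2 of the Data Safety Monitoring Plan (DSMP) repeats the claim and adds one for the SMFQ: "80% power to detect a hazard ratio of 0.52 for time to MDD between the groups as well as >80% power".

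Other sections bear on it:

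- Section 9.6.1, on the comparison of MFY with control: "The study is not expected to produce a quantity of data large enough to have adequate power to detect significant effects".
- Section 9.1: "Statistical hypotheses are not considered relevant to this mechanism".
- Section 9.5.1 makes the time-to-event outcome a PROMIS T-score of 70, with 65 as a fallback: "If too few students reach the target of 70 (2 standard deviations above the population mean").
- Section 9.5, on who is analysed: "Individuals who were unable to attend a class are excluded".

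**The concern.** The power sentence gives a number of participants where a number of events is needed. If about 30% of controls have an event and the hazard ratio is 0.52, fewer than a quarter of the 80 teens will have one. That is far too few for 80% power at this effect size.

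Two further points weaken the sentence. It conflicts with section 9.6.1, which says power will not be adequate for the same comparison. Its only rate is for incident depression in untreated teens, whereas the outcome is now a PROMIS threshold and the comparator is an active program. The documents give no expected rate of reaching 70 or 65 under those conditions.

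What is at stake is planning. The study exists to inform an adequately powered trial. A reader who trusts the 80% could treat a null result as informative, or size the next trial near 80.

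**Working it through.** **Inputs from the documents.** 80 teens, 80% power and hazard ratio (HR) 0.52 (section 9.2.1). Four cohorts with 10 per arm, so 40 per arm (Précis, Design and Outcomes). Control incidence above 30% (section 9.2.1).

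**Assumptions, because the plan is silent.** Two-sided 5% (one-sided 5% also shown), proportional hazards, no dropout, independent participants. The 40%, 50% and 60% incidences are scenarios chosen for this check. They are not figures from the plan.

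**1. Trying to reproduce the stated figure.** |ln 0.52| = 0.654, and its square is 0.4276.

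- Schoenfeld, two-sided 5%: events = 4 × (1.960 + 0.842)² / 0.4276 = 73.4, so 74.
- Schoenfeld, one-sided 5%: 4 × (1.645 + 0.842)² / 0.4276 = 57.8, so 58.
- Freedman, two-sided 5%: 2.802² × (1.52/0.48)² = 78.7, so 79.

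The 80% does not follow from 80 teens and 30% incidence. It does appear if all 80 teens are entered as events: Freedman's formula with 80 events gives a detectable HR of 0.523. This suggests that participants were counted as events. It is an inference, since the documents show no calculation.

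**2. Expected events.** With control incidence p, treated incidence is 1 − (1 − p)^0.52, and events = 40p + 40[1 − (1 − p)^0.52]. At p = 0.30, treated incidence is 1 − 0.70^0.52 = 0.169, so events = 12.0 + 6.8 = 18.8.

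**3. Power.** Power = Φ(√(events/4) × 0.654 − z), with z = 1.960 two-sided or 1.645 one-sided. The simulation used a log-rank test, exponential times, 40 per arm and 8,000 runs per scenario.

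| Control incidence | Events | Power, two-sided 5% | Simulation, two-sided 5% | Power, one-sided 5% |
|---|---|---|---|---|
| 30% | 18.8 | 29% | 28% | 41% |
| 40% | 25.3 | 38% | 37% | 50% |
| 50% | 32.1 | 46% | 44% | 58% |
| 60% | 39.2 | 53% | 52% | 66% |

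**4. Incidence needed for 80% power.** Two-sided 5%: about 98% of controls, with about 86% of the treated arm. One-sided 5%: about 84% and 61%. Even 80% control incidence gives 68% two-sided power, and 90% gives 74%.

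**5. Other readings of the inputs.** Taking 30% as the treated-arm rate gives 31.9 events and 45% power. Taking 80 per arm at 30% incidence gives 52%. Neither reaches 80%.

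**6. Fewer teens analysed.** Section 9.5 drops teens who attended no class. If 36 per arm remain (assumed), two-sided power over 30% to 60% incidence is 27% to 49%. At 32 per arm it is 24% to 45%.

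**7. Precision.** At 30% incidence, before rounding the events, SE(ln HR) = 2/√18.77 = 0.462. The expected 95% interval around 0.52 is 0.52 × exp(±0.905), or about 0.21 to 1.29.

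**8. Size for 74 events.** 74 / (18.77/80) gives about 316 teens at 30% control incidence. At 60% the total is about 152.

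**9. The SMFQ claim.** A difference of 4 with SD 6 and 40 independent teens per arm gives 84% power, so that statement reproduces on those terms.

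**The case against.** The arithmetic is not disputed. The case on the other side is as follows.

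- **Alpha and incidence are open.** The plan states no alpha, and its rate is a floor. With a one-sided 10% test about 42 events are needed, and 80% power is reached at about 64% control incidence. A weekly score crossing 70 or 65 could be common in teens enrolled for depressive symptoms. This stands as a limit on wording: whether 80% is out of reach depends on alpha and on which incidences are plausible. But one-sided 10% appears nowhere in the documents, and it still gives only 55% at 30% incidence and 78% at 60%.
- **Low power is already disclosed.** Sections 9.1 and 9.6.1 say so, and feasibility is the main aim. This limits the consequence. It does not make 9.2.1 correct, and it leaves two sections in contradiction.
- **The study is late.** Section 9.5.1 describes data collection in the past tense, so rewording cannot change the design. True, but the stated figure can still mislead whoever plans the next trial.
- **40 per arm may be too generous.** Sections 4.3.4 and 6.2.2 suggest that the first two cohorts or groups were not randomized. With 30 or 20 per arm, power at 30% incidence would be 23% or 17%. This makes the stated claim worse.
- **The SMFQ figure ignores group delivery.** Fair: the 84% assumes independent teens. This review proposes no change to that sentence, but does not vouch for it under clustering.

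**Conclusion.** The concern holds. The 80% power for HR 0.52 cannot be obtained from the plan's inputs. With two-sided 5%, 40 per arm and full follow-up, power is about 29% at the only incidence the plan names and about 53% at twice that incidence. One-sided 5% gives 41% to 66%. The calculation favours the plan, because it ignores dropout, exclusions, clustering within groups and the use of an active comparator.

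The correction should be made, but its consequence is modest. The outcome comparison is exploratory and nothing in the plan is decided by the 80%. The conclusion rests on an assumed alpha and on incidence scenarios above 30% that the documents do not supply.

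**What to change.** In section 9.2.1 and in DSMP section 7.2, replace only the hazard-ratio claim with wording such as:

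> Assuming a two-sided 5% test, 40 per arm and full follow-up, HR 0.52 needs about 74 events for 80% power. Control incidence of 30%, 40%, 50% or 60% (scenarios) gives about 19, 25, 32 or 39 events and about 29%, 38%, 46% or 53% power. At 30% the expected 95% CI around HR 0.52 is about 0.21 to 1.29. The >30% figure is for untreated incident depression. It is not the rate of reaching PROMIS T-score 70 or 65 with an active comparator, which this study will estimate.

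Add a cross-reference to section 9.6.1 so that the sections agree. If fewer than 40 per arm were randomized, restate the figures for the actual number. Leave the SMFQ sentence in DSMP section 7.2 as it is.

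The cost is wording in two paragraphs and a less favourable stated power for the time-to-event outcome. No added enrolment is needed.

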## 9.3: Definition of Populations

The ITT (Intent to treat) population is any participant randomized to an intervention group, whether or not he/she participates. “Per protocol” populations (“Completers”) are participants who do not formally withdraw.

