## 1.2: Secondary Objectives

### Specific Aim 2

To test the feasibility of an exploratory clinical trial involving a mindful self-compassion intervention, the MFY program (treatment group), and a comparison attention-control among 14-17 year old adolescents (participants may turn 18 after enrollment) with subsyndromal depression. Study results will guide the development of an adequately powered clinical trial in terms of recruitment needs and logistics, equivalence of credibility of the two programs, and participants’ willingness to complete assessment instruments, adhere to study protocols, and complete the study.

#### Purpose 2

Study results will guide the development of an adequately powered clinical trial in terms of recruitment needs and logistics; subjects’ acceptance of the treatment and control programs;

equivalence of credibility of the two programs; and subjects' willingness to complete assessment instruments, adhere to study protocols, and complete the study.

### Specific Aim 3

With feasibility being tested in Aim 2, we will explore primary and secondary outcomes and mediators in response to the MFY program in Aim 3, including time to incident depression by the time of the 36-week follow-up (i.e., MDD-major depressive disorder) (primary outcome); resilience, change in depressive symptoms (secondary outcomes); and rumination, negative cognitive style, and shame (potential mediators).

#### Purpose 3

This study intends to analyze, in an exploratory fashion, the following: incident depression (primary outcome); change in depressive symptoms and resilience (secondary outcomes); and rumination, negative cognitive style, and shame (potential mediators).

Measures are collected at baseline, halfway through the 8-week course, after completion of each 8-week program, at 22 weeks post-program, and at 36 weeks post-program. Analyses are conducted to inform the planning of an adequately powered randomized controlled trial.

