### 9.4.2: Individual stopping rules

If a participant scores above 12 on the combined parent and child SMFQ at any point in the study, s/he will be referred to the study psychologist ([name]) within 24 hours. The study psychologist will then contact the parent of the teen (within 24 hours) to inform the parent of the depression status of the teen. [name] will make an evaluation to determine if s/he can continue in the study and will refer the family for appropriate psychological care.

We have added a safety depression screening measure, the PROMIS pediatric depression scale, which will be administered weekly via REDCap. The Assessment Center at NIH provides a scoring algorithm with REDCap software, enabling use of the measure for safety monitoring. The Project Manager or trained designee will monitor these measures weekly and will alert the team (including the Study Psychologist) to sharp increases in depressive symptoms and depressive symptoms meeting criteria for major depression. If the Study Psychologist confirms the development of major depression, the adolescent will be withdrawn from the study and referred for further care.

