### 9.4.3: Additional Reasons for Withdrawal of a Participant

Additional reasons a participant may withdraw from the study include:

- The adolescent wishes to withdraw from the study;
- Loss of study eligibility (development of major depression);
- Intervening illness or injury making participation difficult;
- The adolescent develops any condition that, in the opinion of the study psychologist, would make continued participation unsafe.

In the unlikely event that a participant is unable to participate in a group setting, s/he may be withdrawn from the study.

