### 9.6.2: Feasibility Analyses

Feasibility will be measured by the following:

1. Acceptance of the treatment and control programs as measured by attendance in 6 of 8 active intervention sessions and 4 of 6 continuation sessions;
2. Equivalence of the credibility of the two programs as measured with the credibility questionnaire;

3. Identification of recruitment challenges and their remedies as measured by:
  - a. the number of individuals screened;
  - b. the proportion of screened adolescents who qualify;
  - c. the number of qualifiers who enroll; and d) the number of enrollees who complete the program—80% completion defined by the acceptance criteria above defines a feasible program;
4. Identification of factors associated with subjects' willingness to adhere to the study protocol such as:
  - a. Location or timing of program classes, or lack of transportation;
  - b. Those not completing the program will be contacted for a telephone interview to evaluate factors leading to dropout.
5. Identification of study components fostering engagement in the study groups and materials.

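### Completers are defined as not formally withdrawing although confirmed MDD forces withdrawal, so that set loses MDD cases, and the 80% completion mark and drop-out comparison are confounded with the outcome

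*Combined protocol and SAP*

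**What the plan says.** Section 9.3 defines two populations. Intent to treat is "any participant randomized to an intervention group, whether or not he/she participates". The per-protocol population, or Completers, "are participants who do not formally withdraw"; no number of sessions is required.

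Section 9.4.2 makes withdrawal follow from confirmed depression: "If the Study Psychologist confirms the development of major depression, the adolescent will be withdrawn from the study and referred for further care". Section 9.4.3 lists development of major depression again, as loss of eligibility.

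Section 9.6.2 measures acceptance of each program by attendance at 6 of 8 weekly and 4 of 6 continuation sessions, and adds that "80% completion defined by the acceptance criteria above defines a feasible program". The Data Safety Monitoring Plan (DSMP, section 8) repeats an 80% criterion for enrollees and states none by arm. Under Program Credibility in 9.6.2, acceptance of randomization is judged by comparing drop-out rates between arms.

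The clinical outcome in Aim 3 (1.2) is "time to incident depression by the time of the 36-week follow-up". Section 9.5.1 makes this operational as "a score of 70 on the PROMIS Pediatric Depression Scale short form t-score". Section 9.5 applies all statistical analyses to randomized adolescents who attended at least one class. On incidence, 9.2.1 states: "Untreated, >30% of adolescents are expected to develop incident depression".

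**The concern.** Completion has two meanings. An adolescent who stops coming but never withdraws formally is a Completer in 9.3 and a non-completer in 9.6.2. An adolescent who attends everything and is then withdrawn for confirmed MDD is never a Completer in 9.3, and is a non-completer in 9.6.2 if the withdrawal comes before the fourth continuation session.

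So the 9.3 set is selected on an event closely tied to the outcome and not on adherence. Any analysis run on it would describe adolescents who mostly did not become depressed, plus some who were barely exposed to the program.

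The planned feasibility measures matter more, because feasibility is the primary goal. A withdrawal that the protocol itself requires is scored as poor acceptance of the program and as drop-out. If MFY prevents depression, the control program will look less acceptable and randomization less well tolerated for that reason alone.

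**Working it through.** The selection in 9.3 follows from the text and needs no arithmetic: confirmed MDD leads to withdrawal, and withdrawal leads to removal from the Completers. The size of the effect on the feasibility measures needs assumptions. The 80% mark is a set criterion, so there is no plan calculation to reproduce.

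Inputs from the documents:
- control incidence 30%, the lower bound in 9.2.1 (an untreated rate, no time horizon);
- hazard ratio 0.52 for MFY (9.2.1), used only to carry the incidence to the other arm;
- 40 per arm (Précis: four cohorts of 10 and 10);
- fourth continuation session at W27, Visit 14 (Table 3; continuation visits at W13, 17, 22, 27, 32, 36). This is the earliest point at which 4 of 6 can be met.

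Assumptions: constant hazard, every case confirmed and withdrawn, perfect attendance otherwise.

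**Expected completion, 30% accruing over 36 weeks**
- Control: 0.70^(27/36) = 76.5%.
- MFY: 0.70^(0.52 × 27/36) = 87.0%.
- Pooled: (76.5 + 87.0)/2 = 81.8%, which leaves 1.8 points for every other reason for missing sessions.

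**Sensitivity to timing and horizon, 30% incidence**

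| Assumption | Control | MFY | Pooled | P(control ≥ 32 of 40) |
|---|---|---|---|---|
| All cases withdrawn before completing | 70.0% | 83.1% | 76.5% | 0.11 |
| W27, 36-week horizon | 76.5% | 87.0% | 81.8% | 0.38 |
| W27, 44-week horizon | 80.3% | 89.2% | 84.8% | 0.61 |
| W27, 52-week horizon | 83.1% | 90.8% | 87.0% | 0.77 |

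Table 3 places the final visit at W36, whereas 6.2.3 and 8.4 place it 36 weeks after the 8-week program, that is week 44. The 44-week row moves the end of follow-up but not the fourth session. Moving both by 8 weeks gives 0.70^(35/44) = 75.3% for control. The 52-week row has no source in the documents and is sensitivity only.

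**Sensitivity to incidence (W27, 36 weeks)**
- 35%: control 72.4%, MFY 84.5%, pooled 78.5%.
- 40%: control 68.2%, MFY 81.9%, pooled 75.1%.
- Expected control completion equals 80% at an incidence of 1 − 0.80^(36/27) = 25.7%.
- At 30% incidence, control falls below 80% only if more than 0.20/0.30, or two thirds, of the cases come before the fourth continuation session.

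**Drop-out comparison by arm**
- MFY incidence over the full horizon: 1 − 0.70^0.52 = 16.9%.
- MDD withdrawals: 40 × 0.30 = 12.0 control and 40 × 0.169 = 6.8 MFY.
- Difference in drop-out from MDD alone: 30.0 − 16.9 = 13.1 points, with no difference in willingness to be randomized.

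**The case against.** Much of the case on the other side stands.

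- No analysis is assigned to the Completers. Section 9.5 uses everyone who attended at least one class, and there an adolescent whose PROMIS event precedes withdrawal still contributes that event. A reader might infer that the depression results will be biased by removal of cases; the documents do not support that.
- The analysed endpoint is PROMIS T 70 (fallback 65), not confirmed MDD. An adolescent can reach T 70 unconfirmed and stay in, or be evaluated through the SMFQ route without reaching it. The two are close (Table 2 labels PROMIS as incident major depression, and DSMP 7.3 equates T 70 with meeting its criteria) but not identical.
- A reader might infer that 80% is out of reach for the control program. That does not follow. The 76.5% is an expected value under assumptions; at that rate 32 of 40 is still reached with probability 0.38. The incidence has no horizon and is labelled untreated, while the control is an active program. The DSMP states the mark for enrollees without splitting by arm, and the pooled figure under the same assumptions is above 80%. The wording in 9.6.2 can fairly be read by program, but not only so.
- An adolescent withdrawn after meeting 6 of 8 and 4 of 6 does count as complete under 9.6.2.
- Reasons for drop-out are collected (9.6.2 item 4; DSMP 7.5), and counting MDD withdrawals as non-completion is legitimate when the question is retention for a later trial.

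What this does not answer is that the 80% mark and the drop-out comparison are planned uses, and neither separates MDD withdrawal from other loss. Collecting the reason does not put it into the measure.

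**Conclusion.** The concern holds in limited form. The conflict between 9.3, 9.5 and 9.6.2, and the removal of confirmed MDD cases from the 9.3 set, are matters of text and rest on no incidence assumption. The harm through the per-protocol set is potential, since nothing planned uses it.

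The effect on feasibility is direct. Both the completion mark and the drop-out comparison mix acceptance with the outcome. At 30% control incidence the loss puts expected control completion at about 70% to 83% before any other non-attendance, and pooled completion at about 82% in the 36-week case (76.5% to 87.0% across the table). The 80% mark is hard to reach for the control program, but not out of reach. These sizes depend on applying an untreated rate to an active control, a constant hazard, every case being withdrawn, and 40 per arm. A lower rate, or later cases, would shrink them.

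**What to change.** 1. In 9.3, define Completers by the attendance part of the rule already in 5.4 and 9.6.2 (6 of 8 and 4 of 6). State how this set and the intent-to-treat set relate to the at-least-one-class set in 9.5, and which analyses, if any, use each.
2. In 9.6.2, including the drop-out comparison under Program Credibility, report withdrawals for confirmed MDD on a separate line by program.
3. Give completion in two forms: with MDD withdrawals counted as non-completers, and with them set apart. Setting apart can mean removing them from the denominator, or scoring them on the same attendance fractions of the sessions held up to withdrawal. The second option needs a stated minimum, so that someone withdrawn after a couple of classes is not counted as a completer.
4. Read acceptance against the 80% mark on the figure that sets them apart, and say whether the mark applies by program or overall. Keep the raw figure for retention planning; it is also the safeguard against over-reading a figure that leaves cases out.

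The withdrawal rule itself is not touched. The cost is a few sentences and one additional reported figure; the data are already collected.
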